2.9. POOLING OF CENTERS FOR STATISTICAL ANALYSES

All participating centers in the study will be pooled together for analysis.

2.10. COMPUTING AND CODING STANDARDS

Activities will be performed using the following tools:

Table, listing, and figure production	SAS Version 9.4 or higher
---------------------------------------	---------------------------

Coding	
AEs	MedDRA Version 23.0 or higher
Medical Histories	MedDRA Version 23.0 or higher
Prior and Concomitant Medications	WHO DDE Version September 2019 or higher
Grading	
AEs	CTCAE Version 4.03
Labs	CTCAE Version 4.03

3. PATIENT INFORMATION

3.1. DISPOSITION OF PATIENTS AND ANALYSIS POPULATIONS

Patient disposition will be summarized in each of the following categories:

- Patients who were randomized:
 - Patients who were randomized but did not receive any dose of study treatment (partial or complete)
 - Patients who were randomized and received at least one dose of study treatment (partial or complete)
- End of blinded treatment:
 - Patients who were still on blinded treatment
 - Patients who discontinued blinded treatment and primary reason for treatment discontinuation
- Patients who proceeded to open-label period (this applies to blinded placebo arm only)
- Survival follow-up status post end of blinded treatment for patients who did not proceed to open-label period:
 - Patients in survival follow-up
 - Patients who have completed survival follow-up
 - Patients who died during survival follow-up
 - Patients who discontinued from the study without starting or completing survival follow-up.
- End of study for patients who did not proceed to open-label period
 - Patients who withdrew from study and primary reason for study withdrawal

A separate disposition summary will be presented for patients who entered open-label period including end of open-label treatment status, survival follow-up status post end of open-label treatment, and end of study status. This applies only to patients randomized to the placebo arm in the blinded phase who entered open-label.

For few patients who were randomized to selinexor in blinded phase and entered open-label selinexor, their end-of-treatment status, date, and reason will be used for end of blinded treatment summary.

3.1.1. Efficacy Populations

The following populations are defined:

- The ***Phase 3 Intent-to-Treat Population (Ph3-ITT)*** will consist of all patients randomized to study treatment in Phase 3, regardless of whether or not they received study treatment. This population will be used for primary analyses of efficacy. Patients

will be analyzed in the treatment arm to which they are randomized and strata assignment at the time of randomization.

- The ***Phase 3 Per-Protocol Population (Ph3-PP)*** will consist of all ITT patients who have received at least 1 dose of study treatment, have no major protocol violations expected to affect assessment of efficacy, and have $\geq 70\%$ compliance to study treatment (see Section 3.4.2 for definition on study treatment compliance). Patients who progress or die are included regardless of duration of time on study treatment. This population will be used for supportive analyses of efficacy. Patients will be analyzed in the treatment arm to which they were randomized.

3.1.2. Safety Populations

For evaluation of safety, the following safety populations are defined:

- The ***Phase 3 Safety Population (Ph3-SAF)*** will consist of all patients in Phase 3 who have received at least one dose of blinded study treatment.
- The ***Phase 2 Safety Population (Ph2-SAF)*** will consist of all patients in Phase 2 who have received at least one dose of blinded study treatment.

Patients in safety populations will be analyzed according to the actual treatment received.

3.1.3. Additional Analysis Populations

- The ***Phase 3 Open-Label Population (Ph3-OL)*** will consist of all patients in Phase 3 who were randomized to placebo in blinded phase, entered open-label period and have received at least one dose of open-label selinexor.
- The ***Phase 2 Intent-to-Treat Population (Ph2-ITT)*** will consist of all patients randomized to study treatment in Phase 2, regardless of whether or not they received study treatment. Patients will be analyzed in the treatment arm to which they were randomized and strata assignment at the time of randomization.
- The ***Phase 2 Open-Label Population (Ph2-OL)*** will consist of all patients in Phase 2 who were randomized to placebo in blinded phase, entered open-label period and have received at least one dose of open-label selinexor.

3.2. DEMOGRAPHICS, MEDICAL HISTORY, AND BASELINE CHARACTERISTICS

Demographics, medical history and baseline characteristics will generally be summarized among the Ph3-ITT, Ph3-SAF, Ph3-OL, Ph2-ITT, Ph2-SAF, and Ph2-OL populations, unless otherwise specified. No formal hypothesis testing will be performed. P-values on demographic, medical history and baseline characteristic data will not be calculated.

In general, the baseline value is defined as latest value prior to the first dose of blinded study treatment.

3.2.1. Demographic Data

Demographic data will be summarized by treatment arm, as well as overall, and will include sex (female, male), race, ethnicity, country, and age at time of consent.

3.2.2. Prior Antineoplastic Therapy

3.2.2.1. Prior Antineoplastic Therapy- Medication

Prior antineoplastic medications will be summarized by treatment arm, as well as overall, and will include the following variables:

- Number of prior antineoplastic regimen (summarized as a continuous variable and as a categorical variable)
- Number of unique prior antineoplastic medications
- Whether patient had prior exposure to eribulin
- Whether patient had prior exposure to trabectedin
- Best response to most recent antineoplastic regimen
- Duration of most recent antineoplastic regimen
- Days since discontinuation of most recent antineoplastic medication to randomization date, which will be calculated as randomization date – stop date of most recent antineoplastic medication + 1

3.2.2.2. Prior Antineoplastic Therapy- Radiation

Prior radiation therapy will be summarized by treatment arm, as well as overall, and will include the following variables:

- Number of patients who received any prior radiation therapy
- Number of prior radiation therapies (summarized as a continuous variable and as a categorical variable, with cut-off of 1 and > 1 prior radiation therapy)
- Best response to most recent radiation therapy

3.2.2.3. Prior Antineoplastic Therapy- Surgery

Prior antineoplastic surgery will be summarized by treatment arm, as well as overall, and will include the following variables:

- Number of patients who received any prior antineoplastic surgery
- Number of prior antineoplastic surgeries (summarized as a continuous variable and as a categorical variable, with cut-off of 1 and > 1 prior surgery therapy)

3.2.3. Medical History

Medical history will be summarized by system organ class (SOC) and preferred term (PT) using the number and percentage of patients who have at least one occurrence of a SOC and PT. The summary will be sorted by alphabetic order in SOC, and further by decreasing frequency of PT within each SOC. When more than one PT has the same frequency, the order of presentation will be alphabetical in PTs.

A separate summary will be provided for ongoing medical history conditions.

3.2.4. Disease History

Disease history data will be summarized by treatment arm, as well as overall, and will include the following variables:

- Time since first initial diagnosis to randomization date
- Time since most recent progression to randomization date
- Stage of current liposarcoma diagnosis

3.2.5. Baseline Characteristics

Baseline characteristics data will be summarized by treatment arm, as well as overall, and will include the following variables:

- Baseline height (cm)/ weight (kg)/ body surface area (m²)/ BMI (kg/m²)
- Baseline ECOG performance status
- Number of unique ongoing medical history (Preferred Terms) per patient
- Number of unique ongoing medications (Anatomical Therapeutic Class [ATC] Level 4 and preferred name) per patient

3.3. PRIOR AND CONCOMITANT MEDICATIONS AND PROCEDURES

Concomitant medications consist of any prescription or over-the-counter preparation, including vitamins, dietary supplements, over-the-counter medications, and oral herbal preparations. Patients may continue their baseline medication(s). Concomitant medications include any medications used to treat symptoms, concomitant diseases such as diabetes, hypertension, etc., AEs and intercurrent illnesses that are medically necessary as part of standard care. All concomitant medication(s) must be reported on the eCRF. Any diagnostic, therapeutic, or surgical procedure performed during the study period should be recorded, including the dates, description of the procedure(s), and any clinical findings, if applicable. Concomitant medication will generally be summarized among ITT and safety populations, unless otherwise specified.

All medications will be coded using the World Health Organization Drug Dictionary Enhanced (WHO DDE).

3.3.1. Prior and Concomitant Medications and Procedures

Prior medications are any treatments received by the patient prior to the first dose of blinded study treatment. Prior medications can be discontinued before first dose of study treatment or can be ongoing during treatment period.

For Ph3-ITT, Ph3-SAF, Ph2-ITT, and Ph2-SAF populations, summaries will be presented among medications concomitant to blinded treatment period i.e., any treatments received by the patient concomitantly during the blinded treatment period from first dose of blinded study treatment to last dose of blinded study treatment + 30 days inclusive, or if applicable, the date of first open-label study treatment exclusive, whichever occurs first. Please refer to Section 2.4 for definitions of blinded treatment period for patients who did or did not proceed to open-label period respectively.

For Ph2-OL and Ph3-OL populations, summaries will be presented among medications concomitantly to open-label treatment period, i.e., any treatments received by the patient concomitantly during the open-label treatment period from first dose of open-label study treatment to last dose of open-label study treatment + 30 days.

Concomitant medications will be summarized according to the WHO DDE by the ATC level 2 (therapeutic level), level 4 (generic level) and preferred name. A patient taking the same drug multiple times will only be counted once.

Note that a medication can be classified as both a prior medication and a concomitant medication.

3.4. EXTENT OF STUDY TREATMENT EXPOSURE AND COMPLIANCE

Extent of study treatment exposure and compliance will be summarized among the Ph3-ITT, Ph3-SAF, Ph3-OL, Ph2-ITT, Ph2-SAF, and Ph2-OL populations, unless otherwise specified.

3.4.1. Extent of Study Treatment Exposure

For Ph3-ITT, Ph3-SAF, Ph2-ITT, and Ph2-SAF populations, summary on exposure will be presented using the following variables:

- Duration of exposure during blinded treatment (summarized as a continuous variable and as a categorical variable), which is defined as the date of last blinded treatment – date of first blinded treatment + 1
- Total dose received during blinded treatment
- Average dose received per week during blinded treatment, which is defined as total dose received during blinded treatment divided by duration of exposure during blinded treatment, presented in mg/week.
- Number and percentage of patients with dose modification including dose reduction and interruption during blinded treatment
 - Number and percentage of patients with dose reduction
 - Number and percentage of patients with drug interruption
- Number and percentage of patients in which blinded treatment was discontinued

For Ph3-OL and Ph2-OL populations, summary on exposure will be presented using the following variables:

- Duration of exposure during open-label treatment (summarized as a continuous variable and as a categorical variable), which is defined as the date of last open-label treatment – date of first open-label treatment + 1
- Total dose received during open-label treatment
- Average dose received per week during open-label treatment, which is defined as total dose received during open-label treatment divided by duration of exposure during open-label treatment, presented in mg/week.
- Number and percentage of patients with dose modification including dose reduction and interruption during open-label treatment

- Number and percentage of patients with dose reduction during open-label treatment
- Number and percentage of patients with drug interruption during open-label treatment
- Number and percentage of patients with open-label treatment discontinued

3.4.2. Treatment Compliance

Study treatment compliance will be summarized descriptively as a quantitative variable, calculated as

$$\frac{\text{number of study treatment doses taken}}{\text{number of study treatment doses prescribed}} \times 100\%.$$

Note that the number of scheduled study treatment doses (selinexor or placebo) does not include doses missed due to treatment interruption or other reasons not related to patient choice. Patients with study treatment compliance < 70% will be excluded from the PP population.

Study treatment compliance will be calculated for blinded treatment period and if applicable, open-label treatment period separately. The number and percentage of patients with blinded study treatment compliance $\geq 70\%$ will be provided among Ph3-ITT, Ph3-SAF, Ph2-ITT, and Ph2-SAF populations. The number and percentage of patients with open-label study treatment compliance $\geq 70\%$ will be provided among Ph3-OL and Ph2-OL populations.

4. EFFICACY

Patient response will be assessed centrally by ICR, according to RECIST v.1.1 (Eisenhauer 2009). Unless otherwise specified, response assessment refers to assessment determined by ICR.

The primary efficacy analyses will be conducted using the ITT population, unless otherwise specified. Efficacy analyses using the PP population will be considered as supportive.

If the interim analysis of unblinded sample size re-estimation is conducted, CHW method will be applied to the primary analysis of the PFS endpoint, with details in Section 1.5.

4.1. PRIMARY EFFICACY ENDPOINTS

4.1.1. Progression-Free Survival (PFS)

Progression-free survival (PFS), defined as the time from date of randomization until ICR-determined PD per RECIST v.1.1, or death due to any cause, whichever occurs first.

The primary analysis of PFS will be performed by treatment arm (selinexor versus placebo) using the Ph3-ITT population. The analysis will be repeated for the Ph3-PP population as a supportive analysis.

Duration is calculated as end date – start date +1. For instance, if a PFS event occurs, then PFS time (in days) is defined as event date – date of randomization +1. If a censoring event occurs, then PFS time is defined as the censoring date – date of randomization +1.

Please refer to Table 4-1 for details on PFS outcome status (PFS event vs. censored) and censoring definitions.

Table 4-1 PFS Outcome and Censoring Definitions

#	Situation	Date of event or censoring	Outcome
1	No baseline disease assessment	Randomization	Censored
2	No adequate post-baseline disease status assessment unless death occurs prior to first post-baseline assessment	Randomization	Censored
3	ICR-determined PD without a gap of 2 or more consecutively missed scheduled disease assessment before PD.	Date of PD	PFS Event
4	Death before ICR-determined PD and without a gap of 2 or more consecutively missed scheduled disease assessment before death.	Date of death	PFS Event
5	No ICR-determined PD or death on or before 
 • Database cut • Withdrawal of informed consent • Lost to follow-up • Date of discontinuation from blinded treatment + 30 days • A gap of 2 or more consecutively missed scheduled disease assessment • Start of new antineoplastic therapy*, whichever occurs first 	Date of last adequate disease assessment prior to the events listed in the left column	Censored

*For the purpose of calculating PFS for blinded treatment, start of open-label selinexor will be considered as initiating a new antineoplastic therapy.

The number and percentage of patients who had a PFS event will be reported. Median PFS with 95% confidence interval (CI) will be summarized using the Kaplan-Meier (KM) method for each treatment arm. The KM curves for PFS will be provided by treatment arm.

A stratified log-rank test will be used to compare the PFS between treatment arms (selinexor versus placebo) for the primary efficacy assessment. The strata will be those used for stratified randomization (i.e., prior eribulin use, prior trabectedin use, number of prior systemic therapies excluding eribulin and trabectedin).

Hazard ratios and its 95% CI will be estimated by a stratified Cox proportional hazards model, with Efron's method of tie handling, with treatment as the factor. The strata will be those used for stratified randomization. A non-stratified log-rank test and a Cox proportional hazards model will be used as sensitivity analyses.

For exploratory purposes, PFS in Ph3-ITT population will also be analyzed:

- In subgroups based on the stratification factors as randomized
- In a sensitivity analysis similar to the primary PFS analysis but where initiation of new antineoplastic therapy is considered as a PFS event
- In a sensitivity analysis similar to the primary PFS analysis but where clinical progression is considered as a PFS event. Clinical progression is defined as the event where a patient discontinues blinded treatment with reason being either disease progression or clinical progression but is not classified as PD by ICR.
- Based on response assessment per investigator

4.2. SECONDARY EFFICACY ENDPOINTS

The secondary efficacy endpoints will be summarized by randomized treatment arm (selinexor vs. placebo), unless otherwise specified.

For time-to-event endpoints, a stratified log-rank test and stratified Cox proportional hazards model analysis will be conducted to assess the effect of selinexor. The strata will be those used for stratified randomization. Median event times with 95% CIs will be estimated based on the KM method for each treatment arm. The KM curves will be provided. The number and percentage of patients with the corresponding events (e.g., death) will be provided. If nominal p-values are computed for those secondary efficacy analyses, they should be interpreted with caution due to potential issues of multiplicity.

For dichotomous endpoints, treatment differences will be tested using the Cochran-Mantel-Haenszel (CMH) test, stratified by the randomization stratification factors. The number and percentage of patients will also be summarized by treatment arm.

4.2.1. Key Secondary Efficacy Endpoints

The following 2 overall survival (OS) endpoints are defined as key secondary endpoints: OS defined as time since randomization until death due to any cause. Patients who are alive will have their OS follow-up time censored at the latest date for which the patient was known to be alive

- OS for non-inferiority in Ph3-ITT population with a non-inferiority margin of HR=1.15.
- OS for superiority in Ph3-ITT population.

Statistical significance of key secondary endpoints will not be claimed until the primary analysis of PFS has reached significance. The key secondary endpoints will be tested using the hierarchical testing procedure to maintain the overall type I error at a 1-sided 0.025 level of significance. More details on the strategy to address multiplicity issues are provided in Section 4.4.

The testing sequence will be:

- OS for non-inferiority in Ph3-ITT population with a non-inferiority margin of HR=1.15.
- OS for superiority in Ph3-ITT population.

4.2.1.1. Overall Survival (OS)

OS is defined as time since randomization until death due to any cause. If death event did not occur during the follow-up period, the patient is censored at the date of discontinuation from the study, or date of last participating visit (e.g., a telephone contact with patient status being alive) on or before database cut-off date, whichever occurs first.

The OS analyses will be conducted among the Ph3-ITT, Ph3-PP, and Ph2-ITT populations.

In sensitivity analysis for OS, the two-stage estimation method will be implemented to assess the impact of cross-over on the effect of selinexor on OS.

For exploratory purposes, OS will be analyzed among Ph3-ITT and Ph2-ITT populations respectively:

- Among the subset of Ph3-ITT population removing patients with the blinded phase treatment unblinded without ICR-confirmed PD
- In a sensitivity analysis in which patients will be censored at the start date of first new antineoplastic therapy including open-label selinexor.
- Among the subset of Ph3-ITT and Ph2-ITT populations, respectively, who did not enter open-label period.
- Assessing the proportion of patients whose OS \geq 12 months (OS12). Patients who were censored before 12 months is considered not meeting the criteria of having OS \geq 12 months. Treatment differences between the selinexor and placebo arms will be tested using the Cochran-Mantel-Haenszel (CMH) test, stratified by the randomization stratification factors. The number and percentage of patients will also be summarized by treatment arm.

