An interim analysis was conducted after 108 PFS events were observed. The interim analysis was designed to allow early stopping for efficacy, futility (non-binding), or sample size re-estimation (up to a maximum of 50% increase in sample size). Based on interim analysis results, DSMB recommended the study to continue.

Approximately 34 months will be required to complete the primary Phase 3 PFS analysis. The primary endpoint analysis will be performed approximately 4 months after enrollment of the last patient, once 209 PFS events are observed. Treatment assignment for all patients will be unblinded at the time of the primary PFS analysis and all Phase 3 patients will be evaluable for assessment of the primary endpoint.

Patients who are on blinded study treatment at the time of the primary PFS analysis at the end of Phase 3 may proceed as follows:

- Patients in the placebo arm may cross over to open-label selinexor (60 mg twice weekly).
- Patients in the selinexor arm will continue selinexor but as open-label treatment.

All patients who have PD while receiving open-label selinexor will discontinue selinexor and be followed for survival, unless the Investigator, in consultation with the Sponsor, believes based on clinical judgement that the patient may derive benefit from continued treatment with selinexor.

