2.3. STUDY TREATMENT DOSING DATE

Study treatment dosing date is the date on which a patient actually received study treatment (selinexor or placebo, partial or complete).

For blinded treatment,

- Except for few patients who were randomized to selinexor in blinded treatment and entered open-label phase, the date of first study treatment is defined as the earliest date of non-zero dose of either selinexor or placebo. The date of last study treatment is defined as the latest date of non-zero dose of either selinexor or placebo before end of blinded treatment.
- For patients who were randomized to selinexor in blinded treatment and entered open-label phase, the date of first study treatment is defined as the earliest date of non-zero dose of selinexor, the date of last study treatment is defined as the latest date of non-zero dose of selinexor, regardless of blinded or open-label phase.

For open-label treatment, the date of first study treatment is defined as the earliest date of non-zero dose of open-label selinexor. The date of last study treatment is defined as the latest date of

non-zero dose of open-label selinexor. This definition only applies to patients who were randomized to placebo in blinded treatment and entered open-label phase.

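### Two exploratory OS analyses mislead as written: OS12 counts patients censored early as 12-month failures, and a subset drops placebo patients who lived long enough to cross over

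*SAP*

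**What the plan says.** SAP 4.2.1.1 introduces a short list of supplementary analyses with "For exploratory purposes, OS will be analyzed among Ph3-ITT and Ph2-ITT populations respectively". Two of them are at issue.

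- **OS12.** The endpoint is the proportion with OS of at least 12 months. On follow-up the SAP says "Patients who were censored before 12 months is considered not meeting the criteria" of OS12. The arms are compared by a stratified CMH test.
- **Subset.** OS is analysed "Among the subset of Ph3-ITT and Ph2-ITT populations, respectively, who did not enter open-label period". SAP 4.2 plans a stratified log-rank test and Cox model for time-to-event endpoints, so this subset would by default receive an HR and a p-value.

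SAP 1.6 describes two locks: one about 4 months after the last enrolment, with efficacy analyses, and a final one after follow-up is complete. It does not say at which lock OS12 is reported. Protocol 14.3.4.2 already foresees 1-year event-free rates with 95% CIs for time-to-event endpoints including OS. The SAP's OS section does not carry them over.

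**The concern.** A patient who is alive at the data cut after 7 months has an unknown 12-month status. The OS12 rule gives that patient the same value as a death. If many patients are in that position, the reported proportions fall below the survival probabilities they are named after, and any real difference shrinks with them.

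The subset conditions on something that happens after randomisation. A placebo patient can enter open-label treatment only by living to centrally determined PD, or by being on blinded treatment at the general unblinding. Removing those patients leaves placebo patients who died early in the comparison, set against a whole selinexor arm. The result would stand beside the planned two-stage crossover analysis and could be misread as a crossover-free effect of selinexor.

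**Working it through.** The documents give no rate, power or HR for either analysis, so there is no planned figure to reproduce.

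**1. OS12 at the primary lock**

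Inputs: 285 Phase 3 patients randomised 2:1 (SAP 1.1), taken as 190:95; accrual about 30 months and analysis about 4 months later, so month 34 (Protocol 7.1). Assumed: uniform accrual, no other loss, and an unstratified two-proportion test in place of CMH.

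- Patients enrolled after month 34 − 12 = 22 have under 12 months of potential follow-up: (30 − 22)/30 = 8/30 = 26.7%, and 0.267 × 285 = 76. With 24 months of accrual it is 8/24 = 33% (95 patients); with 36 months, 8/36 = 22% (63).
- OS12 as defined reads S(12) × 22/30. A true 50% reads 36.7%, 60% reads 44% and 45% reads 33%, so a 15-point difference becomes 11 points.
- Power = Φ[(d − 1.96·SE0)/SE1], with SE0 pooled and SE1 unpooled. For 44% v 33%: pooled p = 0.4033, SE0 = 0.0616, SE1 = 0.0602, and Φ[(0.11 − 0.1207)/0.0602] = Φ(−0.18) = 43%. For 60% v 45% with full follow-up: SE0 = 0.0625, SE1 = 0.0622, and Φ(0.44) = 67%.
- Kaplan-Meier with Greenwood variance at the same month-34 lock, simulated with exponential survival: 62%.
- With 50% in both arms, the simulated two-sided error of the OS12 test is 4.9%.

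This concerns Phase 3 only. Phase 2 enrolment was complete before Phase 3 accrual began, so Phase 2 patients have well over 12 months of potential follow-up by then.

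**2. OS12 at the final lock**

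Follow-up then runs to 24 months after enrolment (SAP 1.4), so no one fails because of the data cut. Only loss or withdrawal before month 12 counts. Assume no effect, true 50%, and 5% (selinexor) v 15% (placebo) lost by month 12.

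| Who is lost | OS12 | Kaplan-Meier |
|---|---|---|
| Unrelated to prognosis | 47.5% v 42.5% | unbiased |
| Patients who would survive 12 months | 45% v 35% | 48% v 45% |
| Patients about to die | 50% v 50% | 53% v 60% |

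First row: 0.50 × 0.95 and 0.50 × 0.85; SE0 = 0.0626, SE1 = 0.0623; one-sided error Φ[(0.05 − 0.1227)/0.0623] = Φ(−1.17) = 12%. With a true 43.5% it is 10.5%. The reverse loss pattern would favour placebo.

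**3. Whom the subset removes**

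- SAP 2.4 gives an open-label treatment period only to patients randomised to placebo. For selinexor patients who continue, it counts open-label dosing in the blinded treatment period.
- SAP 3.1 has the disposition row "Patients who proceeded to open-label period (this applies to blinded placebo arm only".
- SAP 3.1.3 limits the open-label populations to patients who "were randomized to placebo in blinded phase, entered open-label period and have received at least one dose of open-label selinexor".
- SAP 5.1.1.1 follows the same division.

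By the SAP's own usage, then, only placebo crossovers are removed.

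**4. What that selection does**

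Let a share d die before PD, and let a share u of the remaining placebo patients cross over. Ignoring patients still progression-free at unblinding, deaths before PD make up d/[d + (1 − d)(1 − u)] of the placebo subset, against d in the selinexor arm. With d = 10% and u = 60%: 0.10/(0.10 + 0.90 × 0.40) = 22% against 10%. With d = 20%: 0.20/0.52 = 38% against 20%.

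Simulation with no effect on PFS or OS: 190:95, random 60% uptake, 0–20% dying before PD, median time to PD 3–5 months, post-PD median 9–12 months.

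- Final lock: median HR 0.80–1.00. With 10% dying before PD and a post-PD median of 10.5 months it is 0.90 at a 5-month median PD and 0.88 at 3 months.
- Primary lock: 0.76–1.17. Values above 1 arise because placebo patients not yet progressed at the cut stay in, while many who have progressed are removed.
- Full ITT on the same data: 0.99–1.02.
- A second model with frailty and 34–63% of placebo crossing over gave 0.59–0.89, with one-sided rejection of 9–63%.

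**The case against.** **These are exploratory analyses.** They carry no alpha, SAP 4.2 cautions about nominal p-values, and the hierarchical OS tests use the full Phase 3 ITT population (SAP 4.2.1, 4.4). This stands, and it caps the severity at minor. A reader might infer that the key OS tests are compromised; nothing in the documents supports that.

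**The OS12 rule is explicit and treats the arms alike.** This stands for administrative censoring. A reader might infer that the rule manufactures a treatment difference at the primary lock. It does not: randomisation balances the follow-up and the error rate stays near nominal. The cost is understated rates and lost power.

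**Kaplan-Meier is not always better.** If loss falls on patients about to die, OS12 is right and Kaplan-Meier is biased. This stands too, and is why the fix asks for censoring by reason.

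**The subset might look undefined.** SAP 2.3 has rules "For patients who were randomized to selinexor in blinded treatment and entered open-label phase", SAP 3.1 has one "For few patients who were randomized to selinexor in blinded phase and entered open-label selinexor", and SAP 1.1 says of those still on blinded treatment at the primary analysis: "Patients in the selinexor arm will continue selinexor but as open-label treatment". A reader might infer that selinexor patients could be removed as well. But those passages concern dosing dates, treatment status and study conduct, whereas the OS bullet refers to the open-label period, which SAP 2.4 reserves for placebo patients. At most a cross-reference is missing.

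**The bias might look directionless.** A reader might infer that it can go either way in every setting. With placebo-only removal, random uptake and the final lock, the range is 0.80–1.00, so it favours selinexor or is absent. Values above 1 need the primary lock or uptake linked to prognosis.

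**Conclusion.** Both analyses mislead as written; the point is minor.

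OS12 at the primary lock understates 12-month survival by 27% in relative terms in both arms and attenuates a true difference by the same proportion. This rests on 30 months of uniform accrual and a lock 4 months later; the affected share is 22–33% for accrual of 36 to 24 months. At the final lock the rule matters only through loss or withdrawal before month 12. With an assumed 5% v 15% loss unrelated to prognosis, one-sided error is about 10–12%.

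The subset removes placebo crossovers only, so the arms are no longer as randomised and its HR cannot be read as the effect of selinexor on OS. That selection occurs does not depend on the assumed values; its size does. The documents give no rates for crossover uptake, death before PD or loss. At other locks, or if uptake follows prognosis, both size and sign are open: with 75% v 45% uptake the HR was 0.63–0.84 if longer survivors cross over more and 0.96–1.61 if less. Those two ranges cover both locks and both readings of the subset. All of these figures are ranges under assumptions, not predictions.

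**What to change.** **OS12**
- Make the Kaplan-Meier 12-month OS rate per arm, with the difference and its 95% CI, the 12-month analysis, in line with Protocol 14.3.4.2. State the lock at which it is reported.
- Use the same censoring rule as the main OS analysis. That rule must first be reconciled: SAP 4.2.1 and Protocol 14.3.7 censor at the date last known alive, while SAP 4.2.1.1 censors at study discontinuation or last participating visit, whichever is first.
- Report per arm how many patients are censored before month 12 by the data cut and how many by loss or withdrawal, so that informative loss can be judged.
- OS12 is in the protocol's abbreviation list, but the exploratory endpoints are redacted. If it is a protocol endpoint, keep the proportion as a labelled supplementary figure, or document the change in SAP 1.7 and under Protocol 14.4.

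**Subset**
- Add a cross-reference to SAP 2.4 saying that only placebo crossovers are removed.
- Present numbers, deaths and curves without an HR or p-value, or delete the analysis. Rely on ITT OS and the planned two-stage method for crossover.

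The cost is SAP wording and minor programming, with no new data. One exploratory table is relabelled or lost.
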